7.3 Study Population

The intent-to-treat analysis set consists of enrolled subjects who meet the inclusion and exclusion criteria. The safety analysis set consists of subjects who receive treatment at least once. The safety analysis set is also the all treated subjects.

7.3.1 Subject Disposition

A frequency table of all enrolled subjects, broken out by whether or not they were treated, and giving reasons for not being treated, will be produced.

Subject disposition during the treatment period will be summarized. The number and percentage of subjects treated, still on treatment, discontinued from the treatment and reasons for discontinuation will be presented.

By-subject listings will also be produced to accompany the tables on enrollment and the subject disposition table.

In addition, a by-subject listing indicating whether the subject was included in each of the analysis populations will be provided.

7.3.2 Demographic and Subject Characteristics

Demographic and baseline characteristics will be summarized. The following parameters will be summarized; age at the time of informed consent (years), age category at time of informed consent (<65 years, \geq 65 years), and (<75 years, \geq 75 years), gender (Male, Female), race (White, Black/African American, American Indian/Alaska Native, Asian, Native Hawaiian/Other Pacific Islander, Other), ethnicity – for US subjects only (Hispanic/Latino, Not Hispanic/Latino), ECOG performance status (0, 1, 2, 3, 4, 5), time from disease diagnosis to first dose of study drug (months) and lines of prior therapy (2L vs. 3L).

An accompanying by-subject listing of demographic and subject characteristics will be presented for all treated subjects.

7.3.3 Disease Characteristics at Baseline

Baseline disease characteristics will be summarized. The following parameters will be presented to summarize baseline disease:

- Myeloma Serum M-protein (g/dL)
- Myeloma Urine M-protein (mg/24 hours)
- Skeletal Imaging: number of lytic bone lesions
- CT/MRI assessment for extramedullary soft tissue plasmacytoma
- Bone Marrow Aspiration/Biopsy: percentage of plasma cells
- β2 microglobulin (mg/L) (<3.5, ≥3.5-5.5, >5.5)
- Albumin (g/L) ($<3.5, \geq 3.5$)
- ISS Stage at enrollment (I, II, III)
- Myeloma Type
- Disease Status (Relapsed and Refractory, Relapsed, Refractory, Intolerant). Intolerant subjects are classified in the CRF as "Neither Relapsed or Refractory". All categories will be selected from CRF entries.

An accompanying by-subject listing of disease characteristics at baseline will be presented for all treated subjects. Laboratory results will be presented in standard international (SI) units and US units.

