APPENDIX 5 THE INTERNATIONAL STAGING SYSTEM (ISS) FOR MULTIPLE MYELOMA

Stage	Criteria	Median Survival (months)
Stage I	Serum β 2-microglobulin < 3.5 mg/L	62
	Serum albumin $\ge 3.5 \text{ g/dL}$	
Stage II	Not stage I or III	44
	(There are two categories for stage II)	
	serum β 2-microglobulin < 3.5 mg/L but serum albumin < 3.5 g/dL OR	
	β 2-microglobulin 3.5 to < 5.5 mg/L irrespective of the serum albumin level	
Stage III	Serum β 2-microglobulin \geq 5.5 mg/L	29

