7.5 Efficacy

7.5.1 Progression-Free Survival

The primary analysis of this study is to estimate the two definitions of progression free survival (PFS) in all treated patients. The median PFS and 2-sided 95% confidence interval will be caculated via Kaplan-Meier (KM) estimation procedure. The PFS function will be estimated using the KM product limit method and will be displayed graphically. Estimates for 1-year, 2-year, and 3-year PFS rates will be presented along with their associated 95% CIs. These estimates will be come from the KM curve and their standard errors (SEs), for use in constructing CIs, will be computed using Greenwood's formula¹⁷ and on log-log transformation applied on the survivor function.

Analyses of PFS will be conducted based on all treated population, and also by subgroups based on lines of prior therapy (2L/3L groups), or by age group (<65 years, \geq 65 years), and (<75 years, \geq 75 years). Subgroup analysis by ECOG PS (0-1,2), by response to most recent line of therapy (relapsed and refractory, relapsed, refractory, intolerant) and by ISS stage (I,II,III) if albumin and beta 2 microglobulin data are available will be conducted as well. PFS is also evaluated based on 3 levels of response (VGPR or better, PR, SD or MR). PFS will be estimated using the Kaplan-Meier (KM) product limit method and presented using a KM curve.

Time from last tumor assessment to data cut-off in months will be summarized by treatment arm and overall for all treated subjects. Subjects who have a PFS event will be considered as current for this analysis.

A by-subject listing will be presented including PFS duration on all treated population, whether the subject was censored, and if censored, the reason.

All of the analyses will be repreated for primary and secondary definitions of PFS.

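### SAP 7.3.3 cuts baseline albumin at 3.5 g/L where Protocol Appendix 5 uses 3.5 g/dL, and its beta-2-microglobulin bands place exactly 5.5 mg/L on the other side of the stage III line

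*SAP*

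**What the plan says.** SAP 7.3.3 lists the baseline disease characteristics to be summarised. Three entries matter here.

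- Albumin: "Albumin (g/L) ($<3.5, \geq 3.5". There are two classes, split at 3.5, with the unit given as g/L.
- Beta-2-microglobulin: "β2 microglobulin (mg/L) (<3.5, ≥3.5-5.5, >5.5". The top band is strictly above 5.5, so 5.5 itself belongs to the middle band.
- ISS stage at enrolment (I, II, III), as an entry of its own. The SAP gives no rule for deriving it.

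The same section says laboratory results will be shown in both SI and US units; SAP 7.1 and 8.4 say much the same.

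Protocol Appendix 5 defines the ISS. Stage I needs beta-2-microglobulin below 3.5 mg/L and albumin of at least 3.5 g/dL. Stage II has two routes: "serum β 2-microglobulin < 3.5 mg/L but serum albumin < 3.5 g/dL OR" is the first and "β 2-microglobulin 3.5 to < 5.5 mg/L irrespective of the serum albumin level" the second. Stage III is "Serum β 2-microglobulin \geq 5.5 mg/L". Protocol 8.4.1 refers to Appendix 5 for stage at entry.

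SAP 7.5.1 plans a PFS subgroup analysis by ISS stage, which "if albumin and beta 2 microglobulin data are available will be conducted as well". SAP 7.5.2 and 7.5.3 plan the same for OS and ORR.

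**The concern.** The two albumin cuts carry the same number in units that differ by a factor of ten, and no reading reconciles them. The SAP line is an operative instruction to the programmer. Because SI output is required, albumin in g/L will be in the data, and a program that follows the stated unit would run without error and leave the low-albumin class empty.

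Both cohorts are single-arm, and the EPd cohort was sized against an 11-month median PFS described as historical. A reader who wants to know whether the enrolled subjects resemble that reference population has little beyond the baseline prognostic factors. An albumin row with everyone in one class does not help.

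The beta-2-microglobulin bands follow the ISS cut points but reverse the inequality at 5.5, so the band table and the stage table can disagree for a subject recorded at exactly that value.

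**Working it through.** **Inputs from the documents.** Albumin cut of 3.5 g/L and beta-2-microglobulin bands (SAP 7.3.3); albumin cut of 3.5 g/dL and stage III from 5.5 mg/L (Protocol Appendix 5); planned sizes of 60 EPd and 30 EN subjects (SAP 5.1 and 5.2).

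**Step 1: unit conversion.** 1 g/dL = 10 g/L.

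- Appendix 5: 3.5 g/dL × 10 = 35 g/L.
- SAP 7.3.3: 3.5 g/L ÷ 10 = 0.35 g/dL.

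The ratio is 35 / 3.5 = 10, so the SAP cut cannot be reproduced from Appendix 5 in either unit.

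**Step 2: the two albumin cuts applied to values in g/L.**

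| Albumin (g/L) | SAP class as written | Appendix 5 class |
|---|---|---|
| 15 | upper | low |
| 20 | upper | low |
| 50 | upper | upper |

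**Step 3: how many subjects belong in the low class.** The documents give no albumin distribution. Assume a normal distribution with mean 32 to 38 g/L and SD 5 to 7 g/L.

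- Below 3.5 g/L: the largest probability in this range is at mean 32, SD 7: Φ((3.5 − 32)/7) = Φ(−4.07) = 2.3 × 10⁻⁵. Expected count in 60: 60 × 2.3 × 10⁻⁵ = 0.001. The class is empty.
- Below 35 g/L, highest: mean 32, SD 5, Φ((35 − 32)/5) = Φ(0.6) = 0.73, which is 43.5 of 60 and 21.8 of 30.
- Below 35 g/L, lowest: mean 38, SD 5, Φ((35 − 38)/5) = Φ(−0.6) = 0.27, which is 16.5 of 60 and 8.2 of 30.

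**Step 4: beta-2-microglobulin near 5.5 mg/L.**

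| Value (mg/L) | SAP band | ISS by Appendix 5, albumin 40 g/L |
|---|---|---|
| 5.4 | middle | II |
| 5.5 | middle | III |
| 5.6 | top | III |

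Only the value 5.5 differs. The documents give no distribution here either. Assume a lognormal with median 3 to 5 mg/L and log-SD 0.5 to 0.7. With one recorded decimal,

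P(recorded 5.5) = Φ((ln 5.55 − ln median)/SD) − Φ((ln 5.45 − ln median)/SD).

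This runs from 0.0070 (median 3, SD 0.5) to 0.0142 (median 5, SD 0.5). Expected counts are 60 × 0.0070 = 0.42 to 60 × 0.0142 = 0.85 in EPd, and 0.21 to 0.43 in EN. With two recorded decimals the expected count is below 0.1 of 60.

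**Step 5: does ISS stage change?** If stage is derived from Appendix 5, it does not. If stage were instead programmed with a 3.5 g/L albumin cut, a subject with beta-2-microglobulin 3.0 mg/L and albumin 30 g/L would move from stage II to stage I. Subjects with beta-2-microglobulin of 3.5 mg/L or more would keep their stage, because albumin plays no part there: Appendix 5 assigns the middle range "irrespective of the serum albumin level".

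**The case against.** The best defence is that this is a label. The SAP requires US units as well as SI. If the 3.5 cut is applied to values in g/dL, the split is correct and only the printed unit is wrong. The documents do not say which unit the derivation uses, and SAP 9 leaves table details to a separate Data Presentation Plan. A row showing 0% and 100% would also be conspicuous at output review, and by-subject listings of baseline disease characteristics and laboratory data are planned, so the values stay recoverable. All of this stands and limits the consequence. It does not remove the conflict: either the row is uninformative or its stated unit is wrong, and the line needs correcting in both cases.

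Three stronger readings are tempting, and the documents do not support them.

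- A reader might infer that the beta-2-microglobulin bands miss the stage III boundary. They do cut at 5.5 mg/L and differ from Appendix 5 only on the equality.
- A reader might infer that the baseline prognostic table as a whole is wrong. The defect lies in the albumin row and in one equality in another row; ISS stage is a separate row.
- A reader might infer that the ISS subgroups for PFS, OS and ORR will be misstaged, with stage II subjects counted as stage I. The SAP does not derive stage from these display classes, and Protocol 8.4.1 points to Appendix 5, whose cuts are not in dispute. What does stand is that the SAP states no derivation rule, makes the subgroups depend on albumin and beta-2-microglobulin data, and contains no other cuts for those two variables. One sentence would close that gap. A count of misstaged subjects has no basis in the documents.

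**Conclusion.** The albumin cut in SAP 7.3.3 is wrong as written, by a factor of ten against Protocol Appendix 5. That follows from the documents alone. The loss of information in the row is conditional: it requires the cut to be applied to g/L values, and an ordinary range of albumin values, which the documents do not give and which is assumed here. Under that assumption the low class would be empty, when 27% to 73% of subjects belong in it.

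The beta-2-microglobulin discrepancy is also certain, but it touches only values recorded as exactly 5.5 mg/L, fewer than one expected subject per cohort under the assumed distributions.

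The severity is minor. Both defects sit in descriptive baseline rows. The primary PFS and ORR estimates use neither classification, and ISS stage is unaffected if it follows Appendix 5.

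**What to change.** In SAP 7.3.3:

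- Albumin (g/dL): <3.5, ≥3.5; for SI output, <35 and ≥35 g/L.
- Beta-2-microglobulin (mg/L): <3.5, 3.5 to <5.5, ≥5.5.
- Add one sentence stating that ISS stage, for the baseline table and for the subgroups in SAP 7.5.1 to 7.5.3, is derived according to Protocol Appendix 5.

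The cost is two corrected lines, one added sentence and a check of the derivation code. Study conduct, sample size and the primary analyses do not change.

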7.3.4 Prior Anti-Myeloma Therapy

Prior systemic anti-myeloma therapy (which will be identified from the eCRF page "Prior Systemic Therapy for Multiple Myeloma") will be categorized using the WHO drug dictionary and will be summarized. The latest version of the drug dictionary at the time of the analysis will be used.

A summary of the number and percentage of subjects receiving prior stem cell therapy and prior radiotherapy will be presented.

A by-subject listing containing relevant information on prior stem cell transplant, prior radiotherapy and prior systemic anti-myeloma therapy will be provided for all treated subjects.

7.3.5 General Medical History

The number and percentage of subjects with any relevant medical history and by body system will be presented.

7.3.6 Physical Measurements

Physical measurements will not be summarized.

A by subject listing of weight will be provided.

7.4 Extent of Exposure

7.4.1 Study Therapy

Pomalidomide, oral dexamethasone and IV dexamethasone are given at fixed doses and are not adjusted for body surface area or weight. The elotuzumab dose, in contrast, is adjusted for weight. Throughout this SAP, a subject's elotuzumab dose level at a particular time point will refer to the actual dose, in mg/kg, rather than their planned dose. A subject's actual elotuzumab dose level will be computed by dividing their total dose delivered, in mg, as recorded on the "Record of Study Medication - Elotuzumab" eCRF page, by their latest pre-dose weight, in kg, on Day 1 of that cycle.

7.4.1.1 Duration of Study Therapy

The number of cycles of treatment received by subjects will be summarized (using n, mean, STD, median, min, max, q1 and q3).

If there is no treatment interruption, The duration of each treatment (elotuzumab, dexamethasone [oral and IV combined] and pomalidomide), in months, will be calculated as:

(date of last dose of the drug - date of first dose of the drug + 1) / 30.4375

If there is treatment interruption, The duration of each treatment (elotuzumab, dexamethasone [oral and IV combined] and pomalidomide), in months, will be calculated as:

(date of last dose of the drug - date of first dose of the drug – days of treatment interruption + 1)/30.4375

Duration of each of the study treatments will be summarized.

Pomalidomide	Day 1 - Day 21				Day 1	- Day 2	21			Day 1 - I	Day 21	
Elotuzumab*	ţ	ţ	ţ	ţ	ţ	ţ	ţ	ţ	ţ			
Dexamethason e	ţ	ţ	ţ	ţ	ţ	ţ	ţ	ţ	ţ	ţ	Ļ	ţ
Day	1	8	15	22	1	8	15	22	1	8	15	22
Cycle		CJ	vcle 1	•		C	ycle 2	•		Су	cle 3 and	l beyond
* Elotuzumab dose is 10mg/kg Cycle 1 and Cycle 2 then 20 mg/kg Cycle 3 and beyond												

Table 2:	Treatment Schedule

7.4.1.2 Dose Modifications

7.4.1.3 Elotozumab

7.4.1.4 Dose Reduction

Reduction of elotuzumab dosing is not permitted as per the protocol.

7.4.1.5 *Dose Delay*

Dose delays of elotuzumab beyond the allowed dosing window are not permitted as per the protocol. Delays within the allowed dosing window could be for logistical or no reasons and will not be summarized.

7.4.1.6 Dose Omission

An omission for elotuzumab will be calculated based on records from the dosing CRF page. If the interval between the two dosing dates for elotuzumab is > 10 days (in cycles 1, 2 or 3) or > 35 days (from cycle 3 onwards), the dose will be considered to have been omitted.

The number and percentage of subjects with a dose omission, and with 1, 2, 3, or \geq 4 omissions will be summarized. For subjects with an omission, their reason for omission (from the dose modification page of the CRF) will be summarized in the groups: "hematologic toxicity", "non-hematologic toxicity", "AE", "dosing error" and "other". For subjects without an available reason for omission, the category "unknown" will be used.

A by-subject listing for dose omission will be presented for all treated subjects. This listing will include all reported omission per CRF, regardless of whether the subject had a computed omission based on the actual dosing dates.

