4.5.3 Elotuzumab

Elotuzumab will be administered intravenously at a dose of 10 mg/kg weekly (Days 1, 8, 15, and 22 of a 4-week cycle) of the first 2 cycles and starting Cycle 3, elotuzumab will be administered intravenously at a dose of 20 mg/kg of Day 1 of each cycle. A window of -1 to +3 days is permitted in Cycles 1 and 2.

In Cycle 1 and 2, an elotuzumab dose that falls outside of the pre-specified window must be skipped.

In Cycles 3 and beyond, elotuzumab dosing may be delayed for up to 1 week as clinically indicated. If unable to administer within 1 week, then the dose should be skipped and resumption of the elotuzumab continues per the protocol defined schedule.

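### The elotuzumab omission rule puts Cycle 3 under two limits and does not say which cycle an interval belongs to, so every reading misclassifies some doses

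*SAP*

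**What the plan says.** SAP 7.4.1.6 derives omissions from the dosing dates. The condition opens with "If the interval between the two dosing dates for elotuzumab is" and sets the limits at "> 10 days (in cycles 1, 2 or 3) or > 35 days (from cycle 3 onwards". The result feeds a table of subjects with any omission and with 1, 2, 3 or at least 4, broken down by reason; a subject with no recorded reason goes to an unknown category. A separate listing shows every omission reported on the CRF, whether or not the computed rule finds it.

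Protocol 4.5.3 sets the schedule as "10 mg/kg weekly (Days 1, 8, 15, and 22 of a 4-week cycle) of the first 2 cycles", and from Cycle 3 "elotuzumab will be administered intravenously at a dose of 20 mg/kg of Day 1 of each cycle". On timing it says "A window of -1 to +3 days is permitted in Cycles 1 and 2", and "In Cycle 1 and 2, an elotuzumab dose that falls outside of the pre-specified window must be skipped". For later cycles: "In Cycles 3 and beyond, elotuzumab dosing may be delayed for up to 1 week as clinically indicated". Protocol 4.5.8 fixes the start of every cycle relative to Cycle 1 Day 1. SAP 7.4.1.5 says that delays inside the dosing window are not to be summarized.

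**The concern.** Cycle 3 contains one elotuzumab dose, and the next is due 28 days later. A 10-day limit that names Cycle 3 does not fit that interval, and the same sentence also gives Cycle 3 a 35-day limit. A gap runs from one dose to another and can cross a cycle boundary, but the SAP never says which of the two doses decides the cycle. Two programmers could code the sentence differently and produce different tables. The weekly limit also looks as if it was built from the late side of the window only.

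At stake is the elotuzumab compliance summary. Permitted doses could be reported as omissions, probably under the unknown reason because no omission would have been recorded for them, and real omissions could go uncounted.

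**Working it through.** **Inputs.** Scheduled interval of 7 days in Cycles 1 and 2 and 28 days from Cycle 3 (Protocol 4.5.3). Permitted offset from the scheduled date of -1 to +3 days in Cycles 1 and 2 (5 whole-day values) and 0 to +7 from Cycle 3 (8 values; the protocol states no early window there). Because the calendar is anchored, the offsets of neighbouring doses vary independently.

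**Formula.** Gap = scheduled interval + offset of second dose - offset of first dose. CxDy is Cycle x Day y.

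**The plan's own limits.** The SAP gives no derivation, but 7 + 3 = 10 and 28 + 7 = 35 reproduce them. The 35 is the true maximum permitted gap from Cycle 3 on. The 10 leaves out the early day; the true maximum in Cycles 1 and 2 is 7 + 3 + 1 = 11.

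**Within Cycles 1 and 2.**
- No dose skipped: 7 - 1 - 3 = 3 to 7 + 3 + 1 = 11 days. One of 25 offset pairs (-1 then +3) exceeds 10 and is falsely flagged. It cannot arise from C1D1, which is the anchor.
- One dose skipped: 14 - 1 - 3 = 10 to 14 + 3 + 1 = 18 days. One of 25 pairs (+3 then -1) gives 10 and is missed.
- Two consecutive doses skipped: 21 - 4 = 17 to 21 + 4 = 25 days. This is a single gap, so it counts as one omission if each flagged gap is one omission.

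The first two ranges overlap at 10 and 11 days, so no gap cut-off separates them.

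**Around Cycle 3.**
- C2D22 to C3D1, none skipped: 7 on schedule; 7 + 0 - 3 = 4 to 7 + 7 + 1 = 15 permitted. 15 of 40 pairs exceed 10.
- C3D1 to C4D1, none skipped: 28 on schedule; 28 - 7 = 21 to 28 + 7 = 35 permitted. All 64 pairs exceed 10; none exceeds 35.
- C2D22 skipped (C2D15 to C3D1): 14 on schedule; 14 - 3 = 11 to 14 + 7 + 1 = 22. All 40 pairs exceed 10; none exceeds 35.
- C3D1 skipped (C2D22 to C4D1): 35 on schedule; 35 - 3 = 32 to 35 + 7 + 1 = 43. 10 of 40 pairs, including the on-schedule one, do not exceed 35.

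The limits then apply as follows, by which dose sets the gap's cycle and which limit is used for Cycle 3:

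| Gap belongs to | Cycle 3 limit | Permitted C3D1 falsely flagged | Permitted C4D1 falsely flagged | Skipped C3D1 missed | Skipped C2D22 missed |
|---|---|---|---|---|---|
| First dose | >10 | 15 of 40 | 64 of 64 | 0 of 40 | 0 of 40 |
| First dose | >35 | 15 of 40 | 0 of 64 | 0 of 40 | 0 of 40 |
| Second dose | >10 | 15 of 40 | 0 of 64 | 10 of 40 | 0 of 40 |
| Second dose | >35 | 0 of 40 | 0 of 64 | 10 of 40 | 40 of 40 |

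No row is free of error. Later single skips are safe: 56 - 7 = 49 to 56 + 7 = 63 days, always above 35.

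**The case against.** The strongest reply is that the 3 in the first limit was probably meant for the step from C2D22 into C3D1, which is 7 days on schedule, and that the 35-day limit was meant for intervals that start in Cycle 3. SAP Table 2 shows a single Cycle 3 dose, and the SAP document history (version 2.2) records an update to this calculation, which fits that intent without proving it. On that reading no on-schedule dose is flagged.

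This answers a stronger inference that a reader might draw: that nearly every subject dosed in Cycle 4 acquires a false omission and the table becomes uninterpretable. That follows only if the C3D1 to C4D1 gap is assigned to Cycle 3 and the 10-day limit prevails over the 35-day limit given to the same cycle. The SAP does not say so.

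The reply does not rescue the rule. Permitted C3D1 delays are still flagged. A gap across a skipped C3D1 starts in Cycle 2 and ends in Cycle 4: read by its second dose it can be missed at 35 days, and read strictly by the intent above it has no limit at all.

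It is also fair that the Cycles 1 and 2 errors are corner cases, that the listing keeps CRF-reported omissions visible, and that false flags in the unknown category can be noticed. These points limit the harm but do not correct the counts in the table.

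**Conclusion.** The point holds as a defect of definition. Cycle 3 is under two limits, the cycle of an interval is undefined, and each way of resolving this misclassifies some permitted or skipped doses around Cycle 3. In Cycles 1 and 2 the limit errs in both directions, in one of 25 offset pairs each way. The rule also conflicts with SAP 7.4.1.5, because some in-window delays would be tabulated as omissions.

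The consequence is limited to the descriptive elotuzumab omission table: any, 1, 2, 3, at least 4, and reasons. PFS and ORR do not use the rule, and dose intensity (SAP 7.4.1.10) is computed from cumulative dose and dates.

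The pair counts enumerate permitted whole-day offsets; they are not expected frequencies, which the documents do not allow one to estimate. They assume that no early window applies from Cycle 3.

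**What to change.** Replace the gap rule in SAP 7.4.1.6 with a check of each scheduled dose on the calendar anchored to Cycle 1 Day 1. While the subject is on elotuzumab, a dose is omitted if no infusion is recorded within -1 to +3 days of a scheduled Cycle 1 or 2 dose, or within 0 to +7 days of Day 1 from Cycle 3 on. Count each omitted dose separately, so that consecutive skips enter the 1, 2, 3 and at least 4 categories correctly. These are the protocol's own windows, so the check gives no false flags and no misses by construction and agrees with SAP 7.4.1.5.

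Adjusting the cut-offs is not an adequate substitute. Raising the weekly limit to more than 11 days removes the one false flag but misses 3 of 25 single-skip pairs instead of 1 (one at 10 days, two at 11). A limit of more than 15 days for the step into Cycle 3 would miss an on-schedule 14-day gap across a skipped C2D22, and more than 35 days would miss the on-schedule 35-day gap across a skipped C3D1.

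The cost is SAP wording and derivation code; no new data are needed.
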